10.2 Voluntary subject withdrawal

The subject has the right to voluntarily withdraw from the study at any time for any reason without prejudice to her future medical care by the physician or at the institution.

For any subject who withdraws consent, the date and reason for consent withdrawal should be documented. Subject data will be included in the analysis up to the date of the consent withdrawal.

10.3 Procedure for discontinuation

The procedure to be followed at the time a subject either discontinues participation or is removed from the study is:

- (1) Check for the development of adverse events.
- (2) Complete the End-of-Study form and include an explanation of why the subject is withdrawing or withdrawn.

- (3) Attempt to perform follow-up evaluations as outlined above.

11 REGULATORY AND REPORTING REQUIREMENTS

The entities providing oversight of safety and compliance with the protocol require reporting as outlined below. Please refer to Section 20.4 for definitions and Section 20.6 for a grid of reporting timelines.

Adverse events will be tracked from start of treatment through 30 days following the last day of study treatment. All adverse events must be recorded on the toxicity tracking case report form (CRF) with the exception of:

- Baseline adverse events, which shall be recorded on the medical history form

Refer to the data submission schedule in Section 14 for instructions on the collection of AEs in the EDC.

Reporting requirements for Washington University study team may be found in Section 11.1. Reporting requirements for secondary site study teams participating in Washington University-coordinated research may be found in Section 11.2

11.1 Sponsor-Investigator Reporting Requirements

11.1.1 Reporting to the Human Research Protection Office (HRPO) at Washington University

Reporting will be conducted in accordance with Washington University IRB Policies.

Pre-approval of all protocol exceptions must be obtained prior to implementing the change.

11.1.2 Reporting to the Quality Assurance and Safety Monitoring Committee (QASMC) at Washington University

The Washington University Sponsor Investigator (or designee) is required to notify the QASMC of any unanticipated problems involving risks to participants or others occurring at WU or any BJH or SLCH institution that have been reported to and acknowledged by HRPO. (Unanticipated problems reported to HRPO and withdrawn during the review process need not be reported to QASMC).

QASMC must be notified within **10 days** of receipt of IRB acknowledgment via email to [contact]. Submission to QASMC must include the myIRB form and any supporting documentation sent with the form.

For events that occur at secondary sites, the Washington University Sponsor Investigator (or designee) is required to notify the QASMC within 10 days of Washington University notification via email to [contact]. Submission to QASMC must include either the myIRB form and supporting documentation or (if not submitted to myIRB) the date of occurrence, description of the event, whether the event is described in the currently IRB approved materials, the event outcome, determination of relatedness, whether currently enrolled participants will be notified, and whether the informed consent document and/or any study procedures will be modified as a result of this event.

11.1.3 Reporting to the FDA

The conduct of the study will comply with all FDA safety requirements. **PLEASE NOTE THAT REPORTING REQUIREMENTS FOR THE FDA DIFFER FROM REPORTING REQUIREMENTS FOR HRPO/QASMC.** It is the responsibility of the Washington University principal investigator to report to the FDA as follows:

- Report any unexpected fatal or life-threatening suspected adverse reaction (refer to Section 20.4 for definitions) no later than 7 calendar days after initial receipt of the information.
- Report a suspected adverse reaction that is both serious and unexpected (SUSAR, refer to Section 20.4) no later than 15 calendar days after it is determined that the information qualifies for reporting. Report an adverse event (refer to Section 20.4) as a suspected adverse reaction only if there is evidence to suggest a causal relationship between the drug and the adverse event, such as:
 - A single occurrence of an event that is uncommon and known to be strongly associated with drug exposure

- One or more occurrences of an event that is not commonly associated with drug exposure but is otherwise uncommon in the population exposed to the drug
- An aggregate analysis of specific events observed in a clinical trial that indicates those events occur more frequently in the drug treatment group than in a concurrent or historical control group
- Report any findings from epidemiological studies, pooled analysis of multiple studies, or clinical studies that suggest a significant risk in humans exposed to the drug no later than 15 calendar days after it is determined that the information qualifies for reporting.
- Report any findings from animal or in vitro testing that suggest significant risk in humans exposed to the drug no later than 15 calendar days after it is determined that the information qualifies for reporting.
- Report any clinically important increase in the rate of a serious suspected adverse reaction of that listed in the protocol or IB within 15 calendar days after it is determined that the information qualifies for reporting.

Submit each report as an IND safety report in a narrative format or on FDA Form 3500A or in an electronic format that FDA can process, review, and archive. Study teams must notify the Siteman Cancer Center Protocol Development team of each potentially reportable event within 1 business day after initial receipt of the information, and must bring the signed 1571 and FDA Form 3500A to the Siteman Cancer Center Protocol Development team no later than 1 business day prior to the due date for reporting to the FDA.

Each notification to FDA must bear prominent identification of its contents (“IND Safety Report”) and must be transmitted to the review division in the Center for Drug Evaluation and Research (CDER) or in the Center for Biologics Evaluation and Research (CBER) that has responsibility for review of the IND. Relevant follow-up information to an IND safety report must be submitted as soon as the information is available and must be identified as such (“Follow-up IND Safety Report”).

11.1.4 Reporting to Secondary Sites

The Washington University Sponsor-Investigator (or designee) will notify the research team at each secondary site of all unanticipated problems involving risks to participants or others that have occurred at other sites within 10 working days of the occurrence of the event or notification of the Sponsor-Investigator (or designee) of the event. This includes events that take place both at Washington University and at other secondary sites, if applicable. Refer to Section 16.0 (Multicenter Management) for more information.

11.2 Secondary Site Reporting Requirements

The research team at each secondary site is required to promptly notify the Washington University Sponsor-Investigator and designee of all serious adverse events (refer to Section 20.4, Section D) within 1 working day of the occurrence of the event or notification of the secondary site’s PI of the event. This notification may take place via email if there is not yet enough information for a formal written report (using FDA Form 3500a (MedWatch) and Washington University’s cover sheet (Appendix C)). A formal written report must be sent to the Washington University Sponsor-Investigator and designee within 4 calendar days (for fatal or life-threatening suspected adverse reactions) or 11 calendar days (for serious unexpected suspected adverse reactions) of the occurrence of the event or notification of the secondary site’s PI of the event.

The research team at a secondary site is responsible for following its site’s guidelines for reporting applicable events to its site’s IRB according to its own institutional guidelines. The research team at Washington University is responsible for reporting all applicable events to the FDA, CSBio, and Oncovir as needed.

Washington University pre-approval of all protocol exceptions must be obtained prior to implementing the change. Local IRB approval must be obtained as per local guidelines. Washington University IRB approval is not required for protocol exceptions occurring at secondary sites.

11.3 Exceptions to Expedited Reporting

Events that do not require expedited reporting as described in 11.1 include:

- planned hospitalizations
- hospitalization <24 hours
- respite care
- events related to disease progression

Events that do not require expedited reporting must still be captured in the EDC.

12 DATA AND SAFETY MONITORING

In compliance with the Washington University Institutional Data and Safety Monitoring Plan, an independent Data and Safety Monitoring Board (DSMB) will be specifically convened for this trial to review toxicity data. A DSMB will consist of no fewer than 3 members including 2 clinical investigators and a biostatistician. DSMB members must be employed by Washington University, Barnes-Jewish Hospital, or St. Louis Children's Hospital. Like investigators, DSMB members are subject to the Washington University School of Medicine policies regarding standards of conduct. Individuals invited to serve on the DSMB will disclose any potential conflicts of interest to the trial principal investigator and/or appropriate university officials, in accordance with institution policies. Potential conflicts that develop during a trial or a member's tenure on a DSMB must also be disclosed.

Until such a time as the first secondary site enrolls its first patient, a semi-annual DSM report to be prepared by the study team will be submitted to the Quality Assurance and Safety Monitoring Committee (QASMC) semi-annually beginning six months after study activation at Washington University (if at least one patient has been enrolled) or one year after study activation (if no patients have been enrolled at the six-month mark).

The DSM report for the DSMB will be prepared by the study team with assistance from the study statistician, will be reviewed by the DSMB, and will be submitted to the QASM Committee. The DSMB must meet at least every six months beginning six months after study activation at Washington University/beginning six months after enrollment of the first patient at a secondary site, no more than one month prior to the due date of the DSM report to QASMC. This report will include:

- HRPO protocol number, protocol title, Principal Investigator name, data coordinator name, regulatory coordinator name, and statistician
- Date of initial HRPO approval, date of most recent consent HRPO approval/revision, date of HRPO expiration, date of most recent QA audit, study status, and phase of study
- History of study including summary of substantive amendments; summary of accrual suspensions including start/stop dates and reason; and summary of protocol exceptions, error, or breach of confidentiality including start/stop dates and reason
- Study-wide target accrual and study-wide actual accrual including numbers from participating sites
- Protocol activation date at each participating site
- Average rate of accrual observed in year 1, year 2, and subsequent years at each participating site
- Expected accrual end date and accrual by site
- Objectives of protocol with supporting data and list the number of participants who have met each objective
- Measures of efficacy
- Early stopping rules with supporting data and list the number of participants who have met the early stopping rules
- Power analysis and/or interim analysis
- Summary of toxicities at all participating sites
- Abstract submissions/publications
- Summary of any recent literature that may affect the safety or ethics of the study

Further DSMB responsibilities are described in the DSMB charter.

The study principal investigator and coordinator will monitor for serious toxicities on an ongoing basis. Once the principal investigator or coordinator becomes aware of an adverse event, the AE will be reported to the HRPO and QASMC according to institutional guidelines (please refer to Section 11).

Refer to the Washington University Quality Assurance and Safety Monitoring Committee Policies and Procedures for full details on the responsibilities of the DSMB. This is located on the QASMC website at <https://siteman.wustl.edu/research/clinical-research-resources/protocol-office-prmcqasmc/>.

12.1 Developmental therapeutics

Given the nature of this human gene transfer protocol, the principal investigator will monitor and analyze study data as they become available and will review this data on a monthly basis with the Developmental Therapeutics Group at the Siteman Cancer Center. This is an independent group that will provide more rigorous oversight than is routinely provided by the QASMC and the HRPO. The director of the Developmental Therapeutics group will advise [name] in the proper conduct of this study and will review patient treatment and all toxicities in her weekly Phase 1 meeting. In addition, the director of the Developmental Therapeutics group will assist in the oversight of the regulatory and data management personnel involved in this clinical trial.

12.2 Protocol stopping criteria

The principal investigator will closely monitor and analyze study data as they become available and will make determinations regarding the presence and severity of adverse events. The administration of study injections and new enrollments will be halted and the QASMC promptly notified if any of the following events occurs:

- (1) **One** (or more) subject(s) experiences a Grade 3 or 4 adverse event that is classified as probably or definitely related to vaccination;
- (2) **One** (or more) subject(s) experiences a vaccine-related SAE;
- (3) **One** (or more) subject(s) experiences death (other than death related to progressive disease) that occurs within 30 days of neoantigen vaccine administration;
- (4) **Two** (or more) subjects experience the **same** Grade 2 or higher adverse event that is classified as probably or definitely related to vaccination: this criterion applies to fever, vomiting, laboratory abnormalities or other clinical adverse experiences, but does not apply to the subjective local or systemic symptoms of pain/tenderness, malaise, fatigue, headache, chills, nausea, myalgia, or arthralgia.
- (5) Any other observation occurs that in the opinion of the PI results in a recommendation to halt enrollment.

If one of these events does occur, study injections and study enrollments would only resume if review of the adverse events that caused the halt resulted in a recommendation to permit further study injections and study enrollments.

The QASMC, in consultation with the principal investigator, will conduct any review and make the decision to resume or close the study for any Grade 2 or 3 events leading to a halt in the study.

The QASMC, with participation by the principal investigator, will consult with the FDA to conduct the review and make the decision to resume or close the study for all Grade 4 adverse events leading to a halt in the study.

13 STATISTICAL CONSIDERATIONS

13.1 Experimental Design

This is a phase 1, open-label, trial of a neoantigen peptide vaccine strategy. Twenty patients who have had an R0/R1 surgical resection, and who have completed adjuvant chemotherapy will be enrolled. At our institution, pancreatic cancer patients undergo routine staging during (three months) and after adjuvant chemotherapy. If there is no evidence of disease, patients will be eligible for enrollment. After enrollment, exome sequencing of tumor/normal DNA and cDNA-capture sequencing of the tumor will be performed to identify somatic mutations present in the tumor and confirm expression of these mutations at the mRNA level. Epitope prediction algorithms will then be used to prioritize neoantigens for inclusion in neoantigen peptide vaccines, and the neoantigen peptide vaccines will be designed and manufactured. The neoantigen peptide vaccines will be administered starting two to four weeks after the completion of adjuvant chemotherapy. The neoantigen peptide vaccines will be administered at seven time points, Days 1, 4, 8, 15, 22, 50, and 78.

13.1.1 Sample size and accrual

Development of cancer vaccines is currently an area of intense research interest. The traditional paradigm for phase 1 clinical trials has been heavily influenced by phase 1 clinical trials of chemotherapeutic agents, where dose escalation designs are appropriate given the rather narrow dose versus safety concerns of these agents. However, there are major differences between these two classes of therapeutics that have important implications for early clinical development. Specifically, the phase 1 concept of dose escalation to find a maximum-tolerated dose does not apply to most therapeutic cancer vaccines. Most therapeutic cancer vaccines are associated with minimal toxicity at a range that is feasible to manufacture or administer, and there is little reason to believe that the maximum-tolerated dose is the most effective dose [32]. Consistent with recent recommendations published in the statistical literature, the general philosophy of this phase I clinical trial is to facilitate a prompt preliminary evaluation of the safety and immunogenicity of a personalized pancreatic cancer DNA vaccine strategy by testing a fixed dose of vaccine, instead of performing a dose escalation [32]. The sample size (n=15) is chosen to provide a reasonable ability to detect serious adverse events associated with vaccine administration. Based on extensive simulations regarding the sample size for pilot or translational studies, Piantadosi [83] recommended that a sample size of 10 to 20 patients would provide a reasonable precision for estimating preliminary information. We therefore expect that, as detailed below, the proposed sample size for this study will be adequate in estimating both safety and preliminary immune efficacy data. The sample size of n=15 will consist of EVALUABLE patients. Patients who screen fail due to sequencing issues such as poor sample quality will be replaced.

13.1.2 Sample Size Calculations for Safety

One of the primary objectives of this study is to evaluate the safety of the neoantigen peptide vaccines. We have chosen to power the study to provide a reasonable ability to detect serious adverse events associated with vaccine administration.

Sample size calculations for safety are expressed in terms of the ability to detect serious adverse events. The ability of the study to identify serious adverse events is best expressed by the maximum true rate of events that would be unlikely to be observed and the minimum true rate of events that would very likely be observed. Table below shows the probabilities of observing 0, or 2 or more serious adverse events given variety of hypothesized "true" AE rates. If the true rate is at least 15%, for example, there is >90% chance of observing at least 1 serious adverse event among a sample size of n=15 evaluable patients. Conversely, there is only 10% chance that we would observe 2 or more serious adverse event among n=15 evaluable patients if the true rate is less than 3.5%. Although we believe that the true event rate is likely to be quite low, this table presents a range of event rates in an attempt to illustrate the sensitivity of this study to identify potential safety problems with the neoantigen peptide vaccines.

Probability of detecting SAE for different safety scenarios if 15 evaluable patients are enrolled

True Event rate	Pr(0/15)	Pr(2+/15)
0.010	0.860	0.010
0.035	0.586	0.100
0.050	0.463	0.171
0.100	0.206	0.451
0.150	0.087	0.681

13.1.3 Sample Size Calculations for Immunogenicity

The secondary objective and primary scientific endpoint is to assess the prevalence of antigen-specific T cells in the peripheral blood of patients pre- and post-vaccination as measured by flow cytometry and ELISPOT. A power analysis was performed using paired t-test for over time differences (e.g., changes in ELISPOT and multi-parameter flow cytometry). Assuming a moderate correlation between measures taken from the same individual, the designed sample size (n=15 evaluable patients) allows us 80% power at 1-sided 0.05 alpha level to detect a minimum increase of $0.68 \times SD$, where SD represents the standard deviation of measures for immunogenicity. Our preliminary data showed that antigen-specific T cells can be measured with a coefficient of variability (CV=SD/Mean) of approximately 20%. Therefore, if assuming similar variability in the proposed study, the designed sample size provides 80% power to detect a minimal of 15% change in the average antigen-specific T cells. We expect that more power could be achieved because multiple measurements will be taken from the same patient and this allows borrowing information across different time points.

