We then used four experimental systems to confirm that our optimized epitope prediction algorithms accurately prioritized neoantigens. *First*, together with the groups of [name] in Tübingen and [name] in Zurich we detected mLama4 and mAlg8 peptides bound to H-2K^b on d42m1-T3 tumor cells. To our knowledge this is the first time that mutant class I epitopes have been detected bound to tumor cell-associated MHC class I. *Second*, using PE-labeled H-2K^b tetramers carrying mLama4 or mAlg8 peptides, CD8 T cells with specificities for these two epitopes were found to accumulate in d42m1-T3 tumors in α PD-1 treated mice and reached peak values just prior to tumor rejection on day 12. Consistent with the results of the T cell stimulation experiments, mLama4-specific T cells were present in significantly higher numbers in the tumor than mAlg8-specific T cells. No mLama4- or mAlg8-specific T cells were observed in irrelevant, checkpoint blockade-sensitive F244 tumors. *Third*, vaccination of naïve WT mice with mutant-Lama4 or mutant-Alg8 short peptide vaccines (8mer) induced strong CD8 T cell responses that were specific for the mutant, but not the WT epitope (mLama4 = 1650 SFC/10⁶ cells vs. wtLama4 = 75 SFC/10⁶ cells; mAlg8 = 606 SFC/10⁶ cells vs. wtAlg8 = 50 SFC/10⁶ cells). *Fourth*, prophylactic vaccination of mice with long peptides (~30mer) corresponding to either the mLama4 epitope alone, or both the mLama4 and mAlg8 epitopes induced protection against subsequent challenge with d42m1-T3 tumor cells. The combined peptide vaccine was more protective than the vaccine containing the mLama4 long peptide alone (Figure 5).

Of note, immune responses to both mLama4 and mAlg8 were also observed after vaccination with a polyepitope DNA vaccine encoding mLama4, mAlg8, and several additional epitopes. Mice were vaccinated three times and the immune response to mLama4, mAlg8 and control peptides was assessed by ELISPOT using splenocytes from vaccinated mice. Vaccination with polyepitope DNA vaccines induced responses that were similar in magnitude as synthetic long peptide vaccines encoding mLama4 or mAlg8 (data not shown).

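### The claim of 80% power for a 15% change in antigen-specific T cells does not follow from its inputs: they give 13.6%, or at least about 19% if the 20% CV is measurement precision

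*Combined protocol and SAP*

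**What the plan says.** Section 13.1.3 (Sample Size Calculations for Immunogenicity) argues in three steps.

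- Test and size: "A power analysis was performed using paired t-test for over time differences", and "the designed sample size (n=15 evaluable patients) allows us 80% power at 1-sided 0.05 alpha level". The minimum increase is given as 0.68 x SD, "where SD represents the standard deviation of measures for immunogenicity". The calculation rests on "Assuming a moderate correlation between measures taken from the same individual", with no number for that correlation.
- Variability: from preliminary data, "antigen-specific T cells can be measured with a coefficient of variability (CV=SD/Mean) of approximately 20" per cent. No source is cited, and the section does not say whether this is variation between replicates, between repeat samples from one patient, or between patients.
- Conclusion: on the condition that variability in the trial is similar, the design has "80% power to detect a minimal of 15% change in the average antigen-specific T cells".

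Sections 1.2 and 13.1.3 both call this endpoint the primary scientific endpoint. Section 13.1.1 points forward to these calculations when it describes 15 evaluable patients as adequate for preliminary immune data as well as for safety.

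**The concern.** The last step should be a multiplication: 0.68 SD, with an SD of 20% of the mean. The product is not 15%.

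The more consequential question is what the 20% is. A paired t-test depends on how much the change from before to after vaccination varies from patient to patient. The SD of the measure across patients gives that quantity only in combination with the within-patient correlation. The text describes the 20% in the language of how well T cells can be measured. If that means measurement precision, it is not the SD to which a within-patient correlation applies, and the conversion to a percentage fails.

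The 15% is the only detectable effect for this endpoint that is given as a percentage change. A reader of a null result could take it to mean that changes of 15% or more were unlikely to be missed. Whether that is so depends on an input that the section does not define.

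**Working it through.** **Inputs, all from section 13.1.3.** Paired t-test; n = 15 (14 degrees of freedom); one-sided alpha 0.05; power 80%; detectable increase 0.68 SD; CV = SD/mean = 20%; correlation rho called moderate.

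**Formulas.** SD of change = SD x sqrt(2(1 - rho)). Power is the probability that a noncentral t variable with 14 df and noncentrality (mean change / SD of change) x sqrt(15) exceeds 1.761.

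**Step 1: reproduce 0.68 SD.** Power of 80% needs a mean change of 0.675 times the SD of change. At rho = 0.5, sqrt(2 x 0.5) = 1, so the SD of change equals the SD of the measure and the minimum is 0.675 SD. Power at 0.68 SD is 0.805. This step reproduces, and it shows that moderate means a correlation of about 0.5 (0.49 when solved for 0.68). At rho = 0.3 the multiple would be 0.80; at 0.7 it would be 0.52.

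**Step 2: the percentage, if the 20% is the SD across patients.**

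- Detectable change: 0.68 x 20% = 13.6%.
- Power for 15%: 15/20 = 0.75 SD; noncentrality 0.75 x sqrt(15) = 2.90; power 0.868.

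Other conventions do not give 80% for 15% either:

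| Method | Power for 15% |
|---|---|
| Normal approximation, one-sided | 0.896 |
| Normal approximation, two-sided | 0.828 |
| t-test, two-sided | 0.771 |
| t-test on the log scale, one-sided | 0.830 |

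With n = 15 and a CV of 20%, 15% is the 80% point only if rho is about 0.38, which conflicts with the 0.68 SD in the same paragraph.

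**Step 3: the percentage, if the 20% is measurement precision.** The within-patient correlation comes from stable differences between patients, and measurement error contains none. Assume that the errors before and after vaccination are independent and each is 20% of the mean. Then:

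- SD of change from error alone: 20% x sqrt(2) = 28.3% of the mean.
- Detectable change: 0.675 x 28.3% = 19.1%.
- Power for 15%: 15/28.3 = 0.530; noncentrality 0.530 x sqrt(15) = 2.05; power 0.62.

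This is the best case under that reading. If patients' true responses differ with SD t (as a percentage of the mean), the SD of change is sqrt(28.3^2 + t^2). For an assumed t of 20%, that is 34.6%; the detectable change is 23% and power for 15% is 0.48.

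**Step 4: sensitivity to the SD of change.** The documents do not give this SD; the values are assumptions.

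| SD of change, % of mean | Detectable change (0.68 x SD) | Power for 15% |
|---|---|---|
| 20 | 13.6% | 0.87 |
| 50 | 34% | 0.29 |
| 100 | 68% | 0.14 |

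**The case against.** The strongest reply is that the slip favours the plan. On the stated inputs, power for 15% is 0.87, so at least 80% power is true and 15% may simply be 13.6% rounded up. That stands for the across-patient reading: only the description of 15% as the minimum is inexact. A reader might infer from the failed arithmetic that the trial is underpowered for its own target. The stated inputs do not support that.

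A second reply is that the section never says the 20% is assay precision. It defines CV as SD over mean, refers just before to the SD of the immunogenicity measures, and makes the claim conditional on similar variability. That also stands. The measurement reading is an inference from wording, so the sponsor should be asked what the figure is, not told.

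A third reply concerns variation between patients. Vaccines are personalised, and a reader might infer that the 15% holds only if patients differ no more than assay replicates do. That is wrong for a paired test, because stable differences in level cancel; what counts is variation in patients' changes. Nor does the mouse work in section 5.3.2, where two epitopes gave 1650 and 606 SFC per million cells, bear on it. Those values contrast two antigens in mice and are not an estimate of how patients' changes vary.

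The floor of about 19% has conditions of its own. Section 9.2 plans triplicate ELISPOT wells and simultaneous analysis of each set of samples. If the 20% applies to a single well, or if errors are shared within a batch, the contribution from error would be smaller. Section 13.1.3 also expects extra power from repeated time points but puts no number on it. Both are further reasons to define the figure; neither yields 15%.

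Finally, little hangs on the number. Section 13.1.1 chooses n = 15 mainly for detecting serious adverse events, section 13.2 calls the analysis descriptive, and no success rule uses 15%. This limits the weight of the point but does not make the stated figure right.

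**Conclusion.** The point holds in a limited form. The pairing of 15% with 80% power is not what the inputs give on either reading of the CV. Read as the SD across patients with correlation 0.5, the detectable change is 13.6% and power for 15% is about 0.87: inexact and conservative. Read as measurement precision with independent errors at the two times, the detectable change is at least about 19% and power for 15% is at most about 0.62, lower if true responses vary between patients. The documents do not settle which reading applies, so no single corrected figure can be put in the plan's place. The 0.68 SD statement is sound, given a correlation of about 0.5. The matter concerns the stated sensitivity of a secondary endpoint, not the size or conduct of the trial.

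**What to change.** In section 13.1.3:

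1. Give the assumed correlation (0.5) and the resulting SD of within-patient change.
2. Say what the 20% CV measures (replicate wells, repeat samples from one patient, or different patients) and where the preliminary data come from.
3. Replace 15% with 13.6% if the CV is across patients, or with about 19% or more if it is measurement precision.
4. Add one line giving the detectable change if the SD of change is 50% or 100% of the mean (about 34% and 68%), labelled as assumptions.

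The cost is a few sentences, with no change to sample size, procedures or analysis. The downside is that the stated sensitivity may look less favourable.
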